2.0 Goals

2.1 Primary

To assess the clinical benefit of nivolumab in T-cell lymphomas, as measured by objective response rate (ORR) within 12 cycles according to the Lugano Classification Response Criteria (2014) ([Section 11.0](#))

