3.0 Patient Eligibility

3.1 Inclusion Criteria

- 3.11 Age \geq 18 years.
- 3.12 Relapsed or refractory T-cell lymphoma (TCL) biopsy-proven \leq 6 months prior to registration, including the following subtypes:
- Peripheral T-cell lymphoma, not otherwise specified
 - Anaplastic large cell lymphoma, ALK negative, primary systemic type
 - Angioimmunoblastic T-cell lymphoma
 - Extranodal NK/T-cell lymphoma, nasal type
 -
 - Blastic NK-cell lymphoma
 - Enteropathy-associated T-cell lymphoma
 - Hepatosplenic gamma delta T-cell lymphoma
 - Transformed mycosis fungoides
 - T/NK-cell lymphoma, unclassifiable
- 3.13 Measurable disease: Subjects must have at least one lesion that is $>$ 15mm (1.5 cm) in the longest diameter on cross-sectional imaging and measureable in two perpendicular dimensions per computed tomography (spiral CT) or MRI.
- 3.14 After failure of ASCT or after failure of frontline therapy in subjects who declined or are not ASCT candidates
- 3.15 ECOG Performance Status (PS) 0, 1 or 2 ([Appendix I](#))
- 3.16 The following laboratory values obtained \leq 7 days prior to registration.
- White blood cell (WBC) \geq 3000/mm³
 - Absolute neutrophil count (ANC) \geq 1500/mm³
 - Platelet count \geq 100,000/mm³
 - Hemoglobin $>$ 9.0 g/dL
 - Total bilirubin \leq 1.5 x upper limit of normal (ULN) unless elevation due to Gilbert's Syndrome
 - Aspartate transaminase (AST) \leq 2.5 x ULN
 - Creatinine \leq 2.0 mg/dL
 - Calculated creatinine clearance must be \geq 45 ml/min using the Cockcroft-Gault formula below:

Cockcroft-Gault Equation:

$$\text{Creatinine clearance for males} = \frac{(140 - \text{age})(\text{weight in kg})}{(72)(\text{serum creatinine in mg/dL})}$$

$$\text{Creatinine clearance for females} = \frac{(140 - \text{age})(\text{weight in kg})(0.85)}{(72)(\text{serum creatinine in mg/dL})}$$

- 3.17 Negative serum or urine pregnancy test done \leq 7 days prior to registration, for persons of childbearing potential only.

Note: Persons of child-bearing potential (POCBP) must use appropriate method(s) of contraception. POCBP should use an adequate method to avoid pregnancy for 23 weeks (30 days plus the time required for nivolumab to undergo five half-lives) after the last dose of investigational drug.

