11.1 Response Considerations

Schedule of Evaluations: PET/CT scans are required at baseline for all patients. In addition to a baseline PET/CT scan, confirmatory scans should also be obtained post Cycle 4, 8, and 12 of chemotherapy, then a CT scan every 16 weeks thereafter. During observation, CT scan should be obtained every 3 months during the first year to evaluate for disease progression.

Definitions for clinical response for patients with lymphoma are from the recently revised Cheson's et al criteria published in 2014, derived from the original criteria published in 2007. (Cheson et al, 2014)(Cheson et al, 2007). Lymph node measurements should be taken from the CT portion of the PET/CT, or other dedicated CT scans where applicable. Measurement of lymphadenopathy for purposes of assessing for PR will be determined by adding the sum of the products of the maximal perpendicular diameters of measured lesions (SPD). The PPD of a single node is sufficient to evaluate for PD (see Table 11.2). Measurable extranodal disease should be assessed in a manner similar to that for nodal disease. For these recommendations, the spleen is considered nodal disease. Disease that is only assessable (eg, pleural effusions, bone lesions) will be recorded as present or absent only, unless, while an abnormality is still noted by imaging studies or physical examination, it is found to be histologically and pathologically negative.

Response is based on PET/CT based on the revised 2014 Lugano Classification. (Cheson et al, 2014).

Progressive disease is based on either PET-CT based (PMD) or CT based (PD) response criteria. PET confirmation of progressive disease is per physician discretion.

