11.3 Lugano Classification Response criteria (Cheson et al, 2014)

	PET-CT Based Response	CT-Based Response
Complete Response	Complete metabolic response (CMR)	Complete radiologic response (CR) (all of the following)
Lymph nodes and extralymphatic sites	Score 1, 2, or 3* with or without a residual mass on 5PS† It is recognized that in Waldeyer's ring or extranodal sites with high physiologic uptake or with activation within spleen or marrow (eg, with chemotherapy or myeloid colony-stimulating factors), uptake may be greater than normal mediastinum and/or liver. In this circumstance, complete metabolic response may be inferred if uptake at sites of initial involvement is no greater than surrounding normal tissue even if the tissue has high physiologic uptake	Target nodes/nodal masses must regress to ≤1.5 cm in LDi No extralymphatic sites of disease
Nonmeasured lesion	Not applicable	Absent
Organ enlargement	Not applicable	Regress to normal
New lesions	None	None
Bone marrow	No evidence of FDG-avid disease in marrow	Normal by morphology; if indeterminate, IHC negative
Partial Response	Partial metabolic response (PMR)	Partial remission (PR) (all of the following)
Lymph nodes and extralymphatic sites	Score 4 or 5† with reduced uptake compared with baseline and residual mass(es) of any size At interim, these findings suggest responding disease At end of treatment, these findings indicate residual disease	≥50% decrease in SPD of up to 6 target measurable nodes and extranodal sites When a lesion is too small to measure on CT, assign 5 mm X 5 mm as the default value When no longer visible, 0 X 0 mm For a node >5 mm X 5 mm, but smaller than normal, use actual measurement for calculation
Nonmeasured lesions	Not applicable	Absent/normal, regressed, but no increase
Organ enlargement	Not applicable	Spleen must have regressed by >50% in length beyond normal
New lesions	None	None

	PET-CT Based Response	CT-Based Response
Bone marrow	Residual uptake higher than uptake in normal marrow but reduced compared with baseline (diffuse uptake compatible with reactive changes from chemotherapy allowed). If there are persistent focal changes in the marrow in the context of a nodal response, consideration should be given to further evaluation with MRI or biopsy or an interval scan	Not Applicable
No Response or Stable Disease	No metabolic response (NMR)	Stable disease (SD)

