Target nodes/nodal masses, extranodal lesions	Score 4 or 5 with no significant change in FDG uptake from baseline at interim or end of treatment	<50% decrease from baseline in SPD of up to 6 dominant, measurable nodes and extranodal sites; no criteria for progressive disease are met
Nonmeasured lesions	Not applicable	No increase consistent with progression
Organ enlargement	Not applicable	No increase consistent with progression
New lesions	None	None
Bone marrow	No change from baseline	Not Applicable
Progressive disease	Progressive metabolic disease (PMD)	Progressive disease (PD) requires at least 1 of the following
Individual target nodes/nodal masses	Score 4 or 5 with an increase in intensity of uptake from baseline and/or	PPD progression: An individual node/lesion must be abnormal with: LDi >1.5 cm and Increase by ≥50% from PPD nadir and An increase in LDi or SDi from nadir 0.5 cm for lesions ≤2 cm 1.0 cm for lesions >2 cm In the setting of splenomegaly, the splenic length must increase by >50% of the extent of its prior increase beyond baseline (eg, a 15 cm spleen must increase to >16 cm). If no prior splenomegaly, must increase by at least 2 cm from baseline New or recurrent splenomegaly
Extranodal lesions	New FDG-avid foci consistent with lymphoma at interim or end-of-treatment assessment	
Nonmeasured lesions	None	New or clear progression of preexisting nonmeasured lesions
New lesions	New FDG-avid foci consistent with lymphoma rather than another etiology (eg, infection, inflammation). If uncertain regarding etiology of new lesions, biopsy or interval scan may be considered	Regrowth of previously resolved lesions A new node >1.5 cm in any axis A new extranodal site >1.0 cm in any axis; if <1.0 cm in any axis, its presence must be unequivocal and must be attributable to lymphoma

	PET-CT Based Response	CT-Based Response
		Assessable disease of any size unequivocally attributable to lymphoma
Bone marrow	New or recurrent FDG-avid foci	New or recurrent involvement

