- 16.311 Definition: The primary endpoint of this trial is the proportion of complete or partial responses to therapy. A success is defined as a CR or PR as the objective status during therapy. All patients meeting the eligibility criteria who have signed a consent form and have begun treatment will be evaluable for response.
- 16.312 Estimation: The proportion of successes will be estimated by the number of successes divided by the total number of evaluable patients. Confidence intervals for the true success proportion will be calculated.
- 16.32 Secondary Outcome Analyses: These analyses will include all patients meeting the eligibility criteria who have signed a consent form and have begun treatment, including patients who fail to achieve a complete response.
- 16.321 Response: Response rates will be estimated using complete and partial metabolic responses (CMR or PMR) divided by the total number of evaluable patients. All evaluable patients will be used for this analysis. These rates will be compared to the primary endpoint to explore any differences in the measurement method.
- 16.322 Adverse Events: All eligible patients that have initiated treatment will be considered evaluable for assessing adverse event rate(s). The maximum grade for each type of adverse event will be recorded for each patient, and frequency tables will be reviewed to determine patterns. Additionally, the relationship of the adverse event(s) to the study treatment will be taken into consideration.
- 16.323 Progression free survival time is defined for all evaluable patients who have achieved a CR/CMR or PR/PMR as the time from registration to relapse or death due to any cause. The distribution of progression-free survival will be estimated using the method of Kaplan-Meier. In addition, the progression-free survival rate at 5 years after registration will be reported.
- 16.324 Duration of response is defined for all evaluable patients who have achieved a CR/CMR or PR/PMR as the date at which the patient's objective status is first noted to be a CR/CMR or PR/PMR to the earliest date relapse is documented. The distribution of duration of complete response will be estimated using the method of Kaplan-Meier

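### Under the PET column of 11.3, a lesion with low FDG uptake at baseline that never changes can only be called a complete metabolic response; the primary ORR is inflated if that column decides it

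*Combined protocol and SAP*

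**What the plan says.** **Entry.** Inclusion criterion 3.13 asks for at least one lesion of more than "15mm (1.5 cm) in the longest diameter on cross-sectional imaging and measureable in two perpendicular dimensions" on CT or MRI. Nothing in 3.1 or 3.2 refers to FDG uptake. On the baseline scan, 11.1 says "PET/CT scans are required at baseline for all patients", but neither eligibility nor evaluability depends on its result.

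**Response.** Goal 2.1 is "objective response rate (ORR) within 12 cycles according to the Lugano Classification Response Criteria (2014"), with a pointer to Section 11.0. There, 11.1 states "Response is based on PET/CT based on the revised 2014 Lugano Classification". Footnote 2 of the schema also labels SD, CR and PR as PET-CT based. In the PET column of 11.3, CMR is "Score 1, 2, or 3* with or without a residual mass on 5PS". No metabolic response is "Score 4 or 5 with no significant change in FDG uptake from baseline at interim or end of treatment". Partial metabolic response (PMR) likewise needs a score of 4 or 5, with reduced uptake.

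**Analysis.** Under 16.311, "All patients meeting the eligibility criteria who have signed a consent form and have begun treatment will be evaluable for response", and "A success is defined as a CR or PR as the objective status during therapy". Section 16.321 then lists the CMR/PMR rate as a secondary analysis, to be set against the primary endpoint to see whether the measurement method matters.

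**The concern.** The PET column works by elimination, and it has no class for a lesion that was not clearly avid to begin with. Unchanged disease in such a patient is classed as a complete response because every other PET class is closed to it.

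The trial has no control arm, and few responses decide it: 2 in 12 passes the interim and 6 in 35 is positive. The error runs in one direction, because it can add responders but cannot remove any. Under 16.324 the false CMR would also start the clock for duration of response on a date when nothing had happened.

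**Working it through.** **1. Which class fits.** Take a 3 cm node scoring 3 at baseline that still scores 3 and measures 3 cm at the end of Cycle 4 (week 8). There are no new lesions, no avid marrow disease and no progression elsewhere.
- PMR needs a score of 4 or 5: not met.
- No metabolic response needs a score of 4 or 5: not met.
- Progressive metabolic disease needs a score of 4 or 5 with increased uptake, or new avid foci: not met.
- CMR needs a score of 1 to 3, no new lesions and no avid marrow disease: met.

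In the CT column the same node is stable disease, since its SPD has not fallen by 50%. The two columns therefore give opposite answers, and 11.1 has no rule that sends this patient to the CT column.

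**2. The plan's own figures.** The inputs are in 16.2: 12 patients then 35, stop at 1 or fewer successes, positive at 6 or more, p0 = 0.10, p1 = 0.30. With X1 ~ Bin(12, p) and X2 ~ Bin(23, p):

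P(go) = Σ over x = 2 to 12 of P(X1 = x) · P(X2 ≥ 6 − x)

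P(stop) = P(X1 ≤ 1)

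At p = 0.10 this gives 0.098 and 0.659; at p = 0.30 it gives 0.901 and 0.085. These match the table in 16.24, so the design arithmetic is not in dispute.

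**3. Exactly k automatic successes among 35, true ORR 10% in the rest, PET-based primary.** For k = 1, placed at random:
- In the first 12 (probability 12/35): the trial stops only if the other 11 all fail, 0.9^11 = 0.314. P(go) is 0.227.
- In the last 23 (probability 23/35): P(stop) stays at 0.659. P(go) is 0.167, because 5 true successes now suffice.
- Weighted: P(go) = (12/35)(0.227) + (23/35)(0.167) = 0.188. P(stop) = (12/35)(0.314) + (23/35)(0.659) = 0.541.

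| k | P(go) | P(stop at interim) |
|---|---|---|
| 0 | 0.098 | 0.659 |
| 1 | 0.188 | 0.541 |
| 2 | 0.324 | 0.426 |
| 3 | 0.496 | 0.324 |

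**4. As a share f of patients.** The documents give no value for f, so a range is assumed. If every low-uptake patient who would otherwise not respond is counted as CMR, p = 0.10 + 0.90f. If only half are, the rest progressing or showing new lesions, p = 0.10 + 0.45f.

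| f | Expected patients in 35 | P(go), all convert | P(go), half convert |
|---|---|---|---|
| 2% | 0.7 | 0.171 | 0.132 |
| 5% | 1.75 | 0.309 | 0.192 |
| 10% | 3.5 | 0.555 | 0.309 |

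The all-convert column is an upper bound for each f. The half-convert column is illustrative.

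**5. If the primary endpoint is CT-based.** The node is stable disease, and ORR and the decision rule keep 0.098 and 0.901. The false CMR still enters the secondary rate in 16.321. It also enters the responder sets on which PFS (16.323) and duration of response (16.324) are defined, and the sustained-response groups in 16.331, since all three accept CMR or PMR.

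**The case against.** The strongest reply is that the primary endpoint may not be PET-based. Section 16.311 speaks of CR and PR, which in the 11.3 table are the CT labels. Sections 13.1, 16.323 and 16.324 write CR/CMR and PR/PMR when both are meant. Section 16.321 makes the metabolic rate secondary and contrasts it with the primary. On that reading the go/no-go decision is untouched. This stands as a condition on the finding, because the schema and 11.1 say the opposite and the conflict is unresolved.

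Second, 11.1 takes node measurements from the CT portion and uses the SPD to assess PR, so CT has some role. That helps with PR but does not say what to do with a lesion that already meets the CMR row. Section 11.1 also adopts the published criteria by reference. Those are not in the documents, so the gap is shown only for Section 11 as reproduced.

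Third, the CMR row speaks of residual masses and of sites of initial involvement, which suggests that avidity was presumed. Entry also requires relapsed or refractory disease proven by biopsy, and 18.5 asks for documented progression before entry. These points make low baseline uptake less likely without excluding it.

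Two stronger readings should be resisted. A reader might infer that low-uptake disease will be common because nine subtypes are listed, or because the calendar allows the baseline PET-CT up to 28 days before registration while chemotherapy is barred only within the last 2 weeks. The documents give no uptake data by subtype or after treatment, so these facts show only that it is possible. A reader might also take CMR to be allowed explicitly with a mass of any size, but that phrase belongs to the PMR row. The CMR row only says that a residual mass may be present.

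**Conclusion.** The gap is real on the operative text. Within the PET column, unchanged low-uptake disease has no class except CMR, and nothing in the documents redirects it.

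Its reach is conditional. A reader might infer that the primary ORR is inflated as the plan stands. The documents do not settle that, because 11.1 and the schema point to PET while 16.321 points to CT. With a PET-based primary and a true ORR of 10%, one such patient in 35 nearly doubles the false-positive probability, from 0.098 to 0.188, and two take it to 0.324. With a CT-based primary, the damage is limited to the secondary metabolic rate and the PFS, duration-of-response and correlative responder groups.

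The fixed-k figures assume that each such patient is in fact scored CMR. The share-based figures rest on an assumed frequency and, in the all-convert column, are upper bounds rather than predictions. This is a cheap improvement, not a flaw that undermines the design.

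**What to change.** In 11.1:
- Record the Deauville score of the target lesions on the baseline PET-CT.
- Allow PET-based CMR or PMR only where at least one site scored 4 or 5 at baseline.
- Classify every other patient by the CT column of 11.3. Criterion 3.13 already ensures a lesion measurable on CT or MRI, so eligibility need not change.
- Reconcile 11.1 and the schema with 16.311 and 16.321, so that one stated column decides the primary endpoint.

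The cost is protocol wording and one baseline CRF field. The PET-CT is already required, so no scan is added. The downside is that a few patients would be assessed by CT criteria while the rest are assessed by PET. If all patients have an avid site, the change alters no result and documents that the problem did not arise.

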4.0 Test Schedule

4.1 Study Calendar

Tests and procedures	Baseline			Active Monitoring Phase			
	≤14 days prior to Registration	≤7 days prior to Registration	Cycle 1 Day 1 prior to treatment	End of each cycle	Restaging End of Cycles 4, 8, and 12	End of Treatment ¹	Observation Post-treatment followup ²
window				±3 days	±7 days	±7 days	±14 days
History and exam, ECOG PS, Weight	X			X ³	X	X	X
Height	X						
Adverse event assessment	X			X	X	X	X
Pregnancy Test ⁴		X	X	X	X	X	X
B Symptoms ⁵	X						
Hematology: CBC with 5 part differential		X		X	X	X	X
Comprehensive metabolic panel: ALT, AST, total bilirubin, alkaline phosphatase, BUN or serum urea, creatinine, Ca, Mg, Na, K, Cl, LDH, glucose, amylase, lipase, albumin, bicarbonate		X		X	X	X	X
Uric Acid		X					
Erythrocyte sedimentation rate	X						
HBV sAg and HCV Ab or HCV RNA	X						
TSH (with Free T4 and Free T3)		X		X ⁶	X	X	X
ECG	X						

¹ At PD or PMD, withdrawal, removal, or completion of protocol therapy

² Four visits: 1) 35±7 days after last treatment 2) 100-120 days post treatment 3) 230-250 days post treatment 4) 330-390 days post treatment

³ If on physical exam there are any palpable lymph nodes present: Tumor (bidimensional)-measurements by physical exam to be done at end of every cycle, prior to next cycle.

⁴ For persons of childbearing potential only: Serum pregnancy testing is required ≤7 days prior to registration and again ≤24 hrs prior to the first infusion, and then every 28 days (±7 days) during the study therapy period regardless of dosing schedule. After discontinuation from nivolumab, these tests should be repeated at approximately 30 days and approximately 70 days [or more frequently if required by local standard].

⁵ Unexplained persistent fever >38° C (or >100.4° F) in previous month, recurring drenching night sweats during the previous month, and/or unexplained weight loss >10% of body weight in the previous six months.

⁶ Thyroid function testing should be done every third month (±3 days).

Tests and procedures	Baseline			Active Monitoring Phase			
	≤14 days prior to Registration	≤7 days prior to Registration	Cycle 1 Day 1 prior to treatment	End of each cycle	Restaging End of Cycles 4, 8, and 12	End of Treatment ¹	Observation Post-treatment followup ²
window				±3 days	±7 days	±7 days	±14 days
PET-CT ⁷	X				X	X	
CT scan Chest/Abd/Pelvis					X ⁸		X
Mandatory research blood/bone marrow samples (See Section 14.0) ^{R,9}			X ^R	X ^R	X ^R	X ^R	X ^{R,10}

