8.0 Dose Delay Criteria Based on Adverse Events

For events with an attribution of possibly, probably or definitely related to study medication, strictly follow the modifications in this table for the first **two** cycles, until individual treatment tolerance can be ascertained. Thereafter, these modifications should be regarded as guidelines. If multiple adverse events are seen, administer dose based on greatest reduction required for any single adverse event observed. Reductions or increases apply to treatment given in the preceding cycle and are based on adverse events observed since the prior dose.

ALERT: ***ADR reporting may be required for some adverse events (See Section 10)***

8.1 No dose reductions or escalations are allowed for nivolumab.

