8.2 Dose Delay Criteria for Nivolumab

See Management Algorithms ([Appendix II](#))

→ → Use the NCI Common Terminology Criteria for Adverse Events (CTCAE) version 4.0* unless otherwise specified ← ←

CTCAE System/Organ/Class (SOC)	Event	Agent	Action
Investigations	Alanine aminotransferase increased, Aspartate aminotransferase increased, and/or Blood bilirubin increased	Nivolumab	
If a patient has a baseline AST/ALT that is within the normal limits, delay dosing for nivolumab-related \geqGrade 2 (>3-5 x ULN) elevations and start corticosteroids at 0.5 to 1 mg/kg/day prednisone equivalents. Nivolumab may be resumed if the value improves to Grade 1 (≤ 3 x ULN) or better.
 
If a patient has a baseline AST/ALT in the Grade 1 range (ULN to ≤ 3 x ULN), delay dosing for nivolumab-related \geqGrade 3 (>5 to 8 x ULN) elevations and start corticosteroids at 1 to 2 mg/kg/day prednisone equivalents. Nivolumab may be resumed if the value improves to Grade 2 (>3 to 5 x ULN) or better.
 
If a patient has a baseline total bilirubin that is within normal limits, delay dosing for nivolumab-related Grade 2 elevations (>1.5-3 x ULN) and start corticosteroids at 0.5 to 1 mg/kg/day prednisone equivalents. Nivolumab may be resumed if the bilirubin improves to Grade 1 (≤ 1.5 x ULN) or better.
 
If a patient has a baseline total bilirubin that is in the Grade 1 range (ULN to ≤ 1.5 x ULN), delay dosing for nivolumab-related Grade 3 elevations (>3-5 x ULN) and start corticosteroids at 1 to 2 mg/kg/day prednisone equivalents.

CTCAE System/Organ/Class (SOC)	Event	Agent	Action
			
Nivolumab may be resumed if the total bilirubin improves to Grade 2 ($\leq 3 \times$ ULN) or better.
 
Doses of nivolumab should be discontinued permanently for the following LFT abnormalities: AST or ALT $>8 \times$ ULN (Grade 3) or drug-induced liver injury (DILI); Total bilirubin $>5 \times$ ULN (Grade 3) or DIL; concurrent AST or ALT $>3 \times$ ULN and total bilirubin $>2 \times$ ULN. Administer corticosteroids 1 to 2 mg/kg/day prednisone equivalents.
 
Subjects with combined Grade 2 AST/ALT meeting discontinuation parameters: go to event monitoring per Section 4.2.

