Gastrointestinal disorders	Pancreatitis	Nivolumab	
Grade 2: Hold nivolumab until resolution, maximum 3 weeks.
 
If >3 weeks, discontinue nivolumab and patient goes to event monitoring.
 
Grade 3 or Grade 4, hold nivolumab until Grade 2 or better then reintroduce
 
If it recurs, the drug is discontinued and patient goes to event monitoring
 
Any \geqGrade 3 drug-related amylase or lipase abnormality that is not associated with symptoms or clinical manifestations of pancreatitis does not require dose delay
 
The PI should be consulted for \geqGrade 3 amylase or lipase abnormalities

Gastrointestinal disorders	Diarrhea	Nivolumab	
Grade ≥ 2 despite maximal supportive care: Hold drug until resolution to baseline grade. If suspicious and clinically indicated, initiate work up to rule out infectious causes and colitis
 
Grade 3 or 4 despite maximal supportive care: Discontinue drug and start corticosteroids until resolution to baseline and patient goes to event monitoring. If suspicious and clinically indicated, initiate work up to rule out infectious causes and colitis

	Colitis	Nivolumab	
Grade ≥ 2: Hold drug until resolution to baseline grade
 
Grade ≥ 3: Discontinue drug and start

CTCAE System/Organ/Class (SOC)	Event	Agent	Action
			corticosteroids until resolution to baseline grade and patient goes to event monitoring
General disorders and administration site conditions	Fatigue	Nivolumab	Grade 3: Hold drug until Grade 2 or better
Metabolism and nutrition disorders	Hyperglycemia	Nivolumab	Grade 4: Permanently discontinue nivolumab
Respiratory, thoracic and mediastinal disorders	Pneumonitis	Nivolumab	Grade ≥ 2 : Hold drug and start corticosteroids until resolution to baseline grade Grade ≥ 3 : Discontinue nivolumab and initiate treatment with high doses of corticosteroids and patient goes to event monitoring
	Cough	Nivolumab	Grade ≥ 2 : Hold drug and start corticosteroids until resolution to baseline grade Grade ≥ 3 : Discontinue nivolumab and initiate treatment with high doses of corticosteroids and patient goes to event monitoring
	Dyspnea	Nivolumab	Grade ≥ 2 : Hold drug until resolution to baseline grade
All other hematologic and non-hematologic	All other hematologic and non-hematologic	Nivolumab	Grade ≥ 2 : Hold nivolumab until resolution to Grade 1 or baseline, except for lymphopenia and leukopenia NOTE: Grade 3 lymphopenia or leukopenia do not require dose delay

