8.3 Discontinuation Criteria for Nivolumab

Treatment should be permanently discontinued for the following:

- Any Grade 2 drug-related uveitis or eye pain or blurred vision that does not respond to topical therapy and does not improve to Grade 1 severity within the re-treatment period OR requires systemic treatment
- Any Grade 3 non-skin, drug-related adverse event lasting >7 days, with the following exceptions for drug-related laboratory abnormalities, uveitis, pneumonitis, bronchospasm, hypersensitivity reactions, and infusion reactions, and endocrinopathies:
 - Grade 3 drug-related uveitis, pneumonitis, bronchospasm, hypersensitivity reaction, or infusion reaction of any duration requires discontinuation
 - Grade 3 drug-related endocrinopathies adequately controlled with only physiologic hormone replacement do not require discontinuation
 - Grade 3 drug-related laboratory abnormalities do not require treatment discontinuation except those noted below

- Grade 3 drug-related thrombocytopenia >7 days or associated with bleeding requires discontinuation
- Any drug-related liver function test (LFT) abnormality that meets the following criteria require discontinuation:
 - AST or ALT >8 x ULN
 - Total bilirubin >5 x ULN
 - Concurrent AST or ALT >3 x ULN and total bilirubin >2 x ULN
- Any Grade 4 drug-related adverse event or laboratory abnormality, except for the following events which do not require discontinuation:
 - Isolated Grade 4 amylase or lipase abnormalities that are not associated with symptoms or clinical manifestations of pancreatitis and decrease to < Grade 4 within 1 week of onset.
 - Isolated Grade 4 electrolyte imbalances/abnormalities that are not associated with clinical sequelae and are corrected with supplementation/appropriate management within 72 hours of their onset
 - Grade 4 lymphopenia or leucopenia
 - Grade 4 drug-related endocrinopathy adverse events, such as adrenal insufficiency, ACTH deficiency, hyper- or hypothyroidism, or glucose intolerance, which resolve or are adequately controlled with physiologic hormone replacement (corticosteroids, thyroid hormones) or glucose-controlling agents, respectively, may not require discontinuation after discussion with and approval from the Investigator [as allowed by protocol]
- Any dosing interruption lasting >6 weeks with the following exceptions:

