Appendix II Adverse Event Management Algorithms

(excerpted from Nivolumab Investigator Brochure version 15, June 2016)

Hepatic Adverse Event Management Algorithm

Rule out non-inflammatory causes. If non-inflammatory cause, treat accordingly and continue I-O therapy. Consider imaging for obstruction.

[figure not shown]

Patients on IV steroids may be switched to an equivalent dose of oral corticosteroids (e.g. prednisone) at start of tapering or earlier, once sustained clinical improvement is observed. Lower bioavailability of oral corticosteroids should be taken into account when switching to the equivalent dose of oral corticosteroids.

*I-O therapy may be delayed rather than discontinued if AST/ALT ≤ 8 x ULN and T.bili ≤ 5 x ULN. **The recommended starting dose for grade 4 hepatitis is 2 mg/kg/day methylprednisolone IV.

Skin Adverse Event Management Algorithm

Rule out non-inflammatory causes. If non-inflammatory cause, treat accordingly and continue I-O therapy.

[figure not shown]

Patients on IV steroids may be switched to an equivalent dose of oral corticosteroids (e.g. prednisone) at start of tapering or earlier, once sustained clinical improvement is observed. Lower bioavailability of oral corticosteroids should be taken into account when switching to the equivalent dose of oral corticosteroids.

*Refer to NCI CTCAE v4 for term-specific grading criteria.

Neurological Adverse Event Management Algorithm

[figure not shown]
Rule out non-inflammatory causes. If non-inflammatory cause, treat accordingly and continue I-O therapy.

Patients on IV steroids may be switched to an equivalent dose of oral corticosteroids (e.g. prednisone) at start of tapering or earlier, once sustained clinical improvement is observed. Lower bioavailability of oral corticosteroids should be taken into account when switching to the equivalent dose of oral corticosteroids.

Pulmonary Adverse Event Management Algorithm

[figure not shown]
Rule out non-inflammatory causes. If non-inflammatory cause, treat accordingly and continue I-O therapy. Evaluate with imaging and pulmonary consultation.

Patients on IV steroids may be switched to an equivalent dose of oral corticosteroids (e.g. prednisone) at start of tapering or earlier, once sustained clinical improvement is observed. Lower bioavailability of oral corticosteroids should be taken into account when switching to the equivalent dose of oral corticosteroids.

GI Adverse Event Management Algorithm

[figure not shown]

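### Section 3.16 caps AST but not ALT, so a patient with ALT above 3 x ULN is numerically eligible although neither baseline paragraph of the 8.2 hepatic entry covers that value

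*Combined protocol and SAP*

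**What the plan says.** Section 3.16 lists the laboratory values required within 7 days before registration. Two concern the liver: total bilirubin up to 1.5 x ULN (Gilbert's syndrome excepted), and the line beginning "Aspartate transaminase (AST", with a cap of 2.5 x ULN. No criterion in 3.1 or 3.2 names ALT. The study calendar in 4.1 nevertheless has ALT drawn in the same window: "Comprehensive metabolic panel: ALT, AST, total bilirubin, alkaline phosphatase" and further analytes.

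Section 8.0 tells sites, for events at least possibly related to treatment, to "strictly follow the modifications in this table for the first" two cycles, after which the table is guidance. The hepatic entry in 8.2 has one transaminase paragraph for a normal baseline and a second that opens "If a patient has a baseline AST/ALT in the Grade 1 range", defined there as ULN to 3 x ULN. A further paragraph does not depend on baseline: "Doses of nivolumab should be discontinued permanently for the following LFT abnormalities". Its limits are AST or ALT above 8 x ULN, bilirubin above 5 x ULN, drug-induced liver injury, or AST or ALT above 3 x ULN together with bilirubin above 2 x ULN. Section 8.3 repeats the numeric limits for drug-related abnormalities, including "AST or ALT >8 x ULN".

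Two other places may bear on the same patient. The last row of the 8.2 table, "All other hematologic and non-hematologic", holds drug at Grade 2 or worse until Grade 1 or baseline. The footnote to the Appendix II hepatic algorithm says "I-O therapy may be delayed rather than discontinued if AST/ALT ≤ 8 x ULN and T.bili ≤ 5 x ULN".

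**The concern.** The entry criteria and the dosing rules do not match. The dosing rules handle AST and ALT as a pair throughout, and the entry criteria limit only one of them. The plan gives no reason for the difference, and the ALT result is already in hand when the patient is registered.

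What is at stake is who may be dosed and how an early ALT rise is handled. Section 9.5 recognises hepatic toxicity as a potential effect of nivolumab, and safety and tolerability are a secondary goal (2.21). A site treating a patient who enters with ALT above 3 x ULN would turn to the 8.2 baseline paragraphs during the two cycles in which the table is mandatory, and would find that neither describes the patient.

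**Working it through.** The plan states no figure on this point, so there is none to reproduce. The check sets the entry limits against the baseline ranges.

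Inputs, all in multiples of ULN:
- Entry (3.16): AST ≤2.5; ALT no limit.
- 8.2, normal baseline: delay above 3, steroids 0.5 to 1 mg/kg/day, restart at ≤3.
- 8.2, baseline ULN to ≤3: delay above 5, steroids 1 to 2 mg/kg/day, restart at Grade 2 (>3 to 5) or better.
- 8.2 and 8.3, any baseline: permanent stop for drug-related AST or ALT above 8, or above 3 with bilirubin above 2.

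| Baseline value | If this is AST | If this is ALT | 8.2 baseline paragraph |
|---|---|---|---|
| 0.8 | eligible | not barred | normal |
| 2.5 | eligible | not barred | Grade 1 |
| 3.0 | ineligible | not barred | Grade 1 |
| 3.1 | ineligible | not barred | none |
| 4 | ineligible | not barred | none |
| 8.1 | ineligible | not barred | none; above the permanent-stop level |

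1. AST. The highest eligible value is 2.5, and 2.5 < 3, so every eligible AST baseline falls in one of the two paragraphs. There is no gap.
2. ALT. There is no upper limit at entry and the paragraphs end at 3, so every ALT baseline above 3 is numerically eligible and uncovered.
3. Example. With AST 2 and ALT 4 the patient meets 3.16. AST rises fall under the Grade 1 paragraph. The ALT baseline fits neither paragraph, so the two paragraphs supply no ALT delay level, steroid dose or restart level.
4. With an ALT cap of 2.5. Again 2.5 < 3, so the uncovered ALT range among eligible patients is empty.

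Size. The documents do not say how often ALT exceeds 3 x ULN while AST is at most 2.5 x ULN. Section 16.22 caps accrual at 39, so each such patient would be 1/39 = 2.6% of the maximum.

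**The case against.** The strongest objection is that other text may already cover this patient.

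- **Appendix II.** The 8.2 table refers the reader to the management algorithms there. The hepatic figure is not in the text available, and its footnote implies a branch in which treatment is delayed. A reader might infer from the 8.2 paragraphs that the protocol has no delay step for a high ALT baseline, or that the first ALT action is permanent discontinuation. The documents do not support that inference. What can be said is that the visible footnote gives no ALT level at which to start a delay or to restart.
- **Catch-all row.** If the hepatic row does not address the event, a site could fall back on the last row, which gives a hold trigger and a restart at baseline. That reading is open, although transaminases have their own row. On it, a steroid dose is still unspecified, and a baseline of 4 x ULN is already Grade 2 on the scale used in 8.2, so the trigger would turn on attribution to drug.
- **Meaning of AST/ALT.** A site might classify the patient by the AST that qualified them and use the Grade 1 paragraph for both enzymes. That works for ALT between 3 and 5 x ULN. Above 5, the patient enters already beyond that paragraph's delay level, and its restart level lies below their own baseline.
- **Other safeguards.** Liver tests are repeated at the end of each cycle (4.1) and close monitoring is asked for (15.194). The bilirubin delay rules and the permanent stops still apply. Sections 3.23, 3.24, 3.27, 3.28 and the closing clinical-risk rule of 8.3 can keep out or stop such a patient. These reduce the risk, but they rest on judgement or on a diagnosis and set no ALT level.

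Two further inferences also fail. Equal proportional ALT rises from different baselines lead to different actions, but that follows from fixed multiples of ULN and happens among covered patients too: 1 to 2 x ULN triggers nothing, 2.6 to 5.2 triggers delay. Nor would a patient entering above 8 x ULN have to stop at once, because the stop in 8.3 is for drug-related abnormalities.

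**Conclusion.** The point holds as a mismatch between 3.16 and the two baseline paragraphs of the 8.2 hepatic entry. ALT above 3 x ULN is not barred by any numeric criterion, and those paragraphs do not reach it. The finding goes no further: it does not say that the protocol as a whole lacks a delay step, because the Appendix II figure cannot be seen and the catch-all row can be read as a fallback.

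The size is small. The scenario needs a raised ALT with AST at or below 2.5 x ULN and no exclusion on clinical judgement. Its frequency is unknown; that it is low is an assumption. The primary analysis is not affected, because under 16.311 every eligible, consented patient who starts treatment is evaluable. This is a patient-safety refinement that the sponsor could make, not a flaw that undermines the trial.

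**What to change.** In 3.16, replace the AST line with *AST and ALT ≤2.5 x ULN*. This extends the existing limit to the second enzyme and keeps every eligible transaminase baseline below the 3 x ULN ceiling of the 8.2 paragraphs, so 8.2 needs no change.

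The cost is a short wording amendment and an occasional extra screen failure for isolated ALT elevation. No test, visit or sample-size change is needed, because ALT is already in the panel taken within 7 days before registration.
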